2 WEEK EVALUATION

Following 2 weeks of study procedure administrations with the Erchonia® HLS™, the following will be recorded over videoconference or telemedicine with the site investigator and subject:

- Numerical Rating Scale (NRS): Tinnitus Loudness
- Numerical Rating Scale (NRS): Tinnitus Annoyance
- Tinnitus Handicap Inventory (THI)
- Adverse Events Evaluation

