
JUSTIFICATION FOR THE CURRENT CLINICAL STUDY

Tinnitus is a chronic problem affecting about one in every ten Americans. The persistent perception of sound is not only annoying and bothersome, but can affect multiple aspects of an individual's life, disrupting communication and sleep, and causing emotional and social disturbances such as anxiety and depression. At present, there is no cure for tinnitus and most treatment or management options are of limited short-term benefit restricted to the time of application. Low level laser therapy, such as through application of the Erchonia HLS™ Laser, has been shown through numerous prior trials and FDA clearances to effect positive change in numerous areas, including symptom perception arising from neurocognitive disruptions through its inflammatory reduction and neuromodulation properties. Therefore, it follows that application of Erchonia LLLT may help to alleviate the severity of tinnitus symptoms, providing a simple, non-invasive, safe, effective and side-effect free alternative therapy to reducing the severity of symptoms of tinnitus in affected individuals.

STUDY DESIGN

This pilot study is a non-blinded, two-group evaluation of the effect of the Erchonia® HLS™ on providing relief from the symptoms of tinnitus.

SUBJECT GROUPS

There will be two subject groups (Group A and Group B) in this pilot study. All subjects in both groups will be test subjects; that is, all study subjects will receive the active Erchonia® HLS laser device. The only difference between subject groups will be the anatomical area(s) where the Erchonia® HLS laser device is applied.

NON-BLINDED DESIGN

This pilot study will be non-blinded, such that both subjects and the investigator(s) will be aware that they are receiving the study procedures with active (true) Erchonia® HLS laser device.

NON-RANDOMIZED

As this pilot study wherein, all subjects receive the active procedure administrations, this is a non-randomized study design. The Investigator will assign 5 subjects to Group A and 5 subjects to Group B.

SUBJECTS

Recruitment

Subjects will be recruited from among the Principal Investigator's/test site's pool of patients who are currently being treated for, or who are seeking treatment for the symptoms of tinnitus, or from response to the following recruitment materials.

- a) Flyer

WANTED

**ADULTS WITH TINNITUS ONGOING
OVER THE LAST 6 MONTHS FOR A
CLINICAL STUDY OF THE EFFECTS OF
LOW LEVEL LASER LIGHT ON

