The Tinnitus Handicap Inventory (THI) (Newman et al, 1996, Newman et al, 1998) is a 25-item self-report questionnaire that has Functional, Emotional and Catastrophic subscales. It has excellent convergent validity, construct validity and test-retest reliability. The THI takes 10 minutes to complete.

The individual responses to each of the 25 items are recorded as follows:

- ✓ Yes: 4
- ✓ Sometimes: 2
- ✓ No: 0

Individual scores for each question are added for the total THI score ranging from 0 to 100.

Another way of looking at the results of the THI is by Grade determination, as follows:

- *Grade 1 - slight - (THI 0-16)* – Tinnitus only heard in quiet environment, very easily masked. No interference with sleep or daily activities; generally pertains to individuals who are experiencing but are not troubled by tinnitus.
- *Grade 2 - mild - (THI 18-36)* – Tinnitus easily masked by environmental sounds and easily forgotten with activities. May occasionally interfere with sleep but not daily activities.

- *Grade 3 - moderate - (THI 38-56)* – Tinnitus may be noticed even in the presence of background or environmental noise although daily activities may still be performed. Less noticeable when concentrating. Not infrequently interferes with sleep and quiet activities.
- *Grade 4 - severe - (THI 58-76)* – Tinnitus almost always heard, rarely if ever masked. Leads to disturbed sleep pattern and can interfere with ability to carry out normal daily activities. Quiet activities adversely affected. Hearing loss is likely present, but its presence is not essential.
- *Grade 5 - catastrophic - (THI 78-100)* - All tinnitus symptoms at level of severe or worse. Should be documented evidence of medical consultation. Hearing loss is likely present, but its presence is not essential. Associated psychological pathology is likely to be found in hospital or general practitioner records. Given the epidemiological data, grading in this group should be extremely rare.

SECONDARY OUTCOME MEASURES:

Numerical Rating Scale (NRS)

The Numerical Rating Scale (NRS) will be used to capture the self-reported daily impact of Tinnitus Annoyance and Tinnitus Loudness. Zero represents 'no impact at all' whereas the upper limit represents 'the worst impact ever possible'.

NUMERICAL SCALE: TINNITUS ANNOYANCE

How does the subject rate his or her tinnitus annoyance on a scale of 1 to 100? With 1 being "No Annoyance" and 100 being "Worst possible Annoyance".

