TINNITUS ANNOYANCE SCORE: _____ /100

NUMERICAL SCALE: TINNITUS LOUDNESS

How does the subject rate his or her tinnitus loudness on a scale of 1 to 100? With 1 being "No Loudness" and 100 being "Worst possible Loudness".

TINNITUS LOUDNESS SCORE: _____ /100

Subject Satisfaction with Study Outcome

The subject is asked to rate how satisfied he or she is with any change in his or her overall tinnitus following completion of the laser administration procedures with the Erchonia® FX-635™ by using the 5-point Likert scale presented below to respond to the following question: "Overall, how satisfied or dissatisfied are you with any change in your tinnitus following the study procedures with the study laser device?"

- Very Satisfied
- Somewhat Satisfied
- Neither Satisfied nor Dissatisfied
- Not Very Satisfied
- Not at All Satisfied

STUDY PROCEDURE PROTOCOL

PRE-PROCEDURE ACTIVITIES

Pre-procedure activities will be conducted remotely over videoconference or telemedicine.

STUDY QUALIFICATION

SIGNING OF INFORMED CONSENT FORM

The participant will be sent an electronic version of the Informed Consent Form. The PI will remotely video conference with the prospective research participant, presenting and reviewing in detail the items in the informed consent form with the individual and answering any questions he or she may have. When finished, the researcher and participant will electronically sign the consent form and print or download the signed document for archiving.

ASSIGNMENT OF SUBJECT IDENTIFICATION NUMBER

The subject is assigned a unique subject identification number based upon his or her order of entry into the study.

Additional information about the informed consent and subject ID number assignment is contained in a later section of the protocol titled, "SAFETY AND CONFIDENTIALITY ISSUES."

STUDY QUALIFICATION EVALUATION: INCLUSION/EXCLUSION CRITERIA

INCLUSION CRITERIA

To be eligible for study participation, a subject must satisfy each of the following criteria.

- Subjective tinnitus
- Tonal tinnitus.
- Constant tinnitus on-going at least half the time over at least the past 6 months.
- Willing to abstain from other tinnitus-related treatments except prior hearing aid use throughout the study duration.
- Willing and able to refrain from activities or work involving excessive noise exposure without the use of effective hearing protection throughout study participation.
- 18 years of age or older
- Primary language is English

EXCLUSION CRITERIA

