8 WEEK EVALUATION: STUDY ENDPOINT

Following 8 weeks of study procedure administrations with the Erchonia® HLS™, the following will be recorded over videoconference or telemedicine with the site investigator and subject as outlined in the STUDY TEST BATTERY section above. These recordings will form the study endpoint data set from which change from baseline will be evaluated with respect to assessing study outcome.

- Tinnitus Handicap Inventory (THI)
- Numerical Rating Scale (NRS): Tinnitus Loudness
- Numerical Rating Scale (NRS): Tinnitus Annoyance
- Subject Satisfaction With Study Outcome
- Adverse Events Evaluation

ADVERSE EVENTS

At any time throughout the duration of the clinical trial that is necessary, any and all potential adverse events reported by a subject will be reported to the investigator and will be recorded on the case report form, and subsequently evaluated by a suitably qualified independent reviewer for determination of relationship to the study treatment and whether or not any corrective action needs to be taken. All potential adverse events recorded will be appropriately reported to the governing IRB, as applicable.

It is unlikely and not expected that any adverse events will result from implementation of this clinical study protocol. Prior clinical trials using low level laser light have not typically yielded any adverse events or reactions. However, potential adverse events that may feasibly occur from application of

the Erchonia® HLS™ include, but are not necessarily limited to: skin irritation, discoloring, rash, indentations and infection.

PRIVACY AND CONFIDENTIALITY

Records for each subject in this clinical study will be maintained in separate files in a locked filing cabinet at the respective test site. The investigator at the test site will be responsible for ensuring that all records for a subject pertaining to his or her participation in the clinical study are maintained in the subject's file at all times other than when information is being recorded on them.

Copies of all subject case report forms will be made and supplied to Regulatory Insight, Inc. and Erchonia Corporation. Regulatory Insight, Inc. and Erchonia Corporation will maintain these copies in a separate clinical study file that is kept in a locked filing cabinet on their respective premises. The original records will be maintained at the respective test sites.

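### Self-reported outcomes are recorded in remote contacts with the unblinded investigator, and the plan does not say who completes the scales; private completion before each call would cheaply reduce one source of favourable drift

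*Combined protocol and SAP*

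**What the plan says.** All four outcomes listed in the Statistical Analysis section are the subject's own reports. In the Study Test Battery, the THI "is a 25-item self-report questionnaire that has Functional, Emotional and Catastrophic subscales"; the NRS "will be used to capture the self-reported daily impact of Tinnitus Annoyance and Tinnitus Loudness"; and for satisfaction, "The subject is asked to rate how satisfied he or she is with any change in his or her overall tinnitus".

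The 2 Week Evaluation section states that "the following will be recorded over videoconference or telemedicine with the site investigator and subject". The 4 and 8 Week Evaluation sections use the same arrangement. THI and both NRS items are taken at all three visits, and satisfaction at week 8 only. Of the week 8 values the protocol says: "These recordings will form the study endpoint data set from which change from baseline will be evaluated".

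On the investigator's position:

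- Under Non-Blinded Design, "both subjects and the investigator(s) will be aware that they are receiving the study procedures with active" devices.
- Under Non-Randomized, "The Investigator will assign 5 subjects to Group A and 5 subjects to Group B".
- Under Recruitment, subjects may come from the investigator's or site's own patients, or from a flyer or newspaper advertisement.

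Pre-procedure activities are also remote. Inclusion Criteria Part 2 requires a THI total of at least 38 and at least 40 on each NRS item. The later Pre-Procedure Evaluation Phase does not list the THI or NRS again, so the qualifying scores appear to serve as the baseline.

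**The concern.** The person who knows the treatment and chose the group is also present when every efficacy value is recorded. The documents describe no private completion, neutral script or separate assessor for these outcomes. The only independent reviewer mentioned is for adverse events.

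Answers given to a clinician can differ from answers given alone. If that difference changes between entry and follow-up, it enters the change from baseline. All 10 subjects receive the active device, so nothing in the design can separate such a shift from a device effect. The Purpose of Study section aims to determine effectiveness, and the Statistical Analysis section says the results may help to develop a controlled study. An inflated change could therefore carry over into the planning of that study.

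**Working it through.** The documents give no figure for reporting bias, no SD of change and no sample size calculation, so there is no plan figure to reproduce. The check is mainly one of reasoning.

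**1. Who completes the scales.** The text says that values are recorded with the investigator and subject. It does not say whether the investigator reads out the items or the subject fills in a form during the contact. The annoyance prompt reads "How does the subject rate his or her tinnitus annoyance on a scale of 1 to 100", and the loudness prompt has the same form. Third-person wording fits a form filled in by an assessor. The satisfaction question is put to the subject in the second person, and the THI items are not reproduced. The evidence for interviewer administration is therefore limited to the two NRS prompts.

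**2. What survives in the change score.** Let the reported score at time t be the true score plus a reporting error b(t). Then:

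reported change = true change + [b(follow-up) − b(baseline)]

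If the investigator's presence has the same effect at both times, the bracket is zero. Only a shift matters. Lower scores are better, so a negative bracket looks like improvement. Two pressures point that way:

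- At entry, higher scores are needed to qualify, so b(baseline) may be positive.
- After treatment, the subject reports to the investigator running the study, so b(follow-up) may be negative.

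The cancellation assumes that baseline is taken in the same way as follow-up. The documents say that both are remote, but they name the investigator's part in recording the scales only at follow-up.

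**3. Scale of the instrument.** THI items score 4, 2 or 0, so one response step is 2 points. A step on two items is 2 × 2 = 4 points, and on four items 4 × 2 = 8 points. Grades 2, 3 and 4 start at 18, 38 and 58, which is 20 points apart. This shows how sensitive the score is; it does not estimate the bias.

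**4. Illustration, with assumptions that are not in the documents.** Take n = 10, a true change of 0, a net shift d towards improvement, an SD of THI change s from 10 to 25, and a two-sided paired t-test at 0.05. The plan does not name this test. The noncentrality is d√n/s; for d = 4 and s = 10 it is 4 × √10/10 = 1.26. The chance of a falsely significant improvement is P(T > 2.262), where T has 9 degrees of freedom and that noncentrality:

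| SD of change | d = 0 | d = 4 | d = 8 | 95% CI half-width |
|---|---|---|---|---|
| 10 | 2.5% | 20.4% | 61.6% | 7.2 |
| 15 | 2.5% | 11.4% | 32.6% | 10.7 |
| 20 | 2.5% | 8.2% | 20.4% | 14.3 |
| 25 | 2.5% | 6.6% | 14.6% | 17.9 |

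The half-width is 2.262 × s/√10, for example 2.262 × 10/√10 = 7.2. A modest shift would matter if the data were tested, but sampling error at n = 10 is of similar size or larger.

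**The case against.** The strongest reply is that the study is an exploratory pilot with descriptive reporting and no success criteria, that baseline is collected remotely too, and that the open, uncontrolled design is the larger threat whatever the mode of collection. Much of this stands. It limits the weight of the point, and it means that only a shift over time can bias the change. It does not remove the point, because the entry thresholds and the post-treatment setting give a reason for a shift in one direction.

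A reader might also infer more than the documents support:

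- *That the investigator interviews the subject on every scale.* This is not stated. Subject completion during the contact also fits the text.
- *That the contact is always by video.* Telemedicine is allowed as well.
- *That the investigator is usually the subject's clinician.* Advertising is also permitted and no proportions are given, so the most that can be said is that this may be so.
- *That the comparison of A with B is biased.* Unequal prompting is possible, but nothing shows that the investigator favours one group.
- *That bias is present and can be sized.* The THI arithmetic and the table show sensitivity under assumptions, not a realised bias.
- *That satisfaction adds to bias in the change from baseline.* It is asked once, at week 8, and has no baseline.

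**Conclusion.** The point holds as a risk of bias combined with a gap in the specification. Unblinded, investigator-attended recording of self-reports is stated for all follow-up visits, the mode of completion is left open, and no safeguard is described. Any shift between entry and follow-up would probably favour apparent improvement and could not be told apart from a device effect. Its size is unknown and cannot be derived from the documents.

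The conclusion rests on two readings: that the qualifying scores serve as baseline, and that no private completion is provided for elsewhere. The weight is low to moderate. The point is worth acting on because the remedy is cheap, not because the mode of recording is the main weakness of an open study without controls.

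**What to change.** Amend the qualification and pre-procedure sections and the 2, 4 and 8 Week Evaluation sections as follows:

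- The subject completes the THI and both NRS items alone, on an electronic or mailed form, before each evaluation call: qualification/baseline and weeks 2, 4 and 8.
- The satisfaction rating is added to that form at week 8 only.
- The form is locked before the investigator joins. The call is used for adverse events and to check completeness; any blank item is completed by the subject alone and flagged as late.
- The NRS prompts are reworded in the first person.

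The cost is a form and a reminder. Consent is already electronic and subjects already keep treatment logs at home, so no extra visit or staff is needed. The downside is a small risk of a late or incomplete form, which the call can catch.

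The change removes only the part due to the investigator's presence. A subject who wants to qualify can still score high in private, and open-label expectation and regression to the mean from the entry thresholds remain. The report should say so.

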4 WEEK EVALUATION

Following 4 weeks of study procedure administrations with the Erchonia® HLS™, the following will be recorded over videoconference or telemedicine with the site investigator and subject:

- Numerical Rating Scale (NRS): Tinnitus Loudness
- Numerical Rating Scale (NRS): Tinnitus Annoyance
- Tinnitus Handicap Inventory (THI)
- Adverse Events Evaluation

8 WEEK EVALUATION: STUDY ENDPOINT

Following 8 weeks of study procedure administrations with the Erchonia® HLS™, the following will be recorded over videoconference or telemedicine with the site investigator and subject as outlined in the STUDY TEST BATTERY section above. These recordings will form the study endpoint data set from which change from baseline will be evaluated with respect to assessing study outcome.

- Tinnitus Handicap Inventory (THI)
- Numerical Rating Scale (NRS): Tinnitus Loudness
- Numerical Rating Scale (NRS): Tinnitus Annoyance
- Subject Satisfaction With Study Outcome
- Adverse Events Evaluation

ADVERSE EVENTS

At any time throughout the duration of the clinical trial that is necessary, any and all potential adverse events reported by a subject will be reported to the investigator and will be recorded on the case report form, and subsequently evaluated by a suitably qualified independent reviewer for determination of relationship to the study treatment and whether or not any corrective action needs to be taken. All potential adverse events recorded will be appropriately reported to the governing IRB, as applicable.

It is unlikely and not expected that any adverse events will result from implementation of this clinical study protocol. Prior clinical trials using low level laser light have not typically yielded any adverse events or reactions. However, potential adverse events that may feasibly occur from application of

the Erchonia® HLS™ include, but are not necessarily limited to: skin irritation, discoloring, rash, indentations and infection.

PRIVACY AND CONFIDENTIALITY

Records for each subject in this clinical study will be maintained in separate files in a locked filing cabinet at the respective test site. The investigator at the test site will be responsible for ensuring that all records for a subject pertaining to his or her participation in the clinical study are maintained in the subject's file at all times other than when information is being recorded on them.

Copies of all subject case report forms will be made and supplied to Regulatory Insight, Inc. and Erchonia Corporation. Regulatory Insight, Inc. and Erchonia Corporation will maintain these copies in a separate clinical study file that is kept in a locked filing cabinet on their respective premises. The original records will be maintained at the respective test sites.

Subjects' identities will be kept confidential by assigning each subject a subject ID upon acceptance into the study. The subject ID will comprise the investigator's two initials (first and last name initials) and a three-digit number that will be based upon the subject's order of entry into the clinical study. For example, with Principal Investigator [name] would have a subject ID of JB101-JB110. Neither the study Sponsor nor Regulatory Insight, Inc. will receive any additional identifying information about a subject and will therefore have no way of linking a subject ID to a particular subject and his or her results.

MONITORING OF THE CLINICAL STUDY

Prior to commencement of the study, the trained study Monitor(s) will provide formalized and documented training to the conduct of clinical studies in general, to the specifics of the current clinical study protocol, to the identification and reporting of adverse events and protocol deviations and to the correct set-up, operation and treatment application of the Erchonia® HLS to the study population for all study staff involved parties. A formalized Clinical Trial Monitoring Plan will be in place for real time, remote and on-site monitoring, as applicable, that will be strictly followed to ensure on-going compliance and accuracy of procedures at the test site(s).

STATISTICAL ANALYSIS

As this is an observational pilot study only, there are no pre-established primary or secondary outcome measures and no pre-established individual subject or study success criteria; rather it is the goal of this study to explore the potential benefits of low level laser therapy administration with the Erchonia HLS™ in reducing symptoms related to tinnitus, the results of which may be used to assist in developing a controlled clinical study to formally evaluate the study goal in the future.

Outcomes Evaluated

The following outcomes will be evaluated as recorded across study duration:

- Tinnitus Handicap Inventory (THI)
- Numerical Rating Scale (NRS): Tinnitus Loudness
- Numerical Rating Scale (NRS): Tinnitus Annoyance
- Satisfaction Rating

Co-Variate Evaluation

Consideration will be given to the role of demographic variables and procedure group assignment.

Evaluation Time Points

Evaluation time points are baseline (pre-treatment), two weeks, four weeks, and 8 weeks study endpoint.

Statistical Procedures

Outcome data will be presented descriptively and through trending. One-way ANCOVA analysis to evaluate the change in measurements across evaluation points may be applied, as applicable.

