EXPECTED RESULTS

Following completion of the study procedure administration protocol with the Erchonia® HLS™, it is anticipated that compared with baseline, subjects will show a reduction in tinnitus symptoms at study endpoint evaluation.

HISTORY OF THE CLINICAL STUDY

WIRB PRO NUM: 20182570: A double-blind, placebo-controlled randomized evaluation of the effect of the Erchonia® FX-635™ on the relief of tinnitus symptoms

DEVICE DESCRIPTION

The Erchonia® HLS Laser will be self-administered by the subject at home, for a total of 56 treatment administrations: Daily administration for 8 consecutive weeks. Each HLS administration will last a total of 10 minutes.

The Erchonia HLS Laser is a hand-held single diode, variable hertz laser that is portable, self-contained, lightweight, and battery operated.

The Erchonia HLS Laser emits a 640 nanometer (nm) wavelength with a tolerance of ± 10 nanometer. The diode is classified by the Center for Devices and Radiological Health (CDRH) as Class II laser diode in accordance with IEC 60825-1, compliant to 21CFR1040 via Laser Notice#50.

An internal battery that is recharged using an external inductive charging base powers the laser. The internal battery powers the specially created and patented electronic diode that emits a $<10\text{mW}$ red laser beam.

The HLS Laser has the following specifications:

Power	7.5 mW ± 1.00 mW
Wavelength	640 nm ± 10 nm
Waveform	Variable Hertz
Joules	4.5 Joules per treatment administration
Energy Source	Single electronic diode, with patented optics

Power Supply	100-240 V ac; 50-60 Hz electrical outlet, lithium-ion Polymer battery
Duty Cycle	50%
Energy Delivery	Handheld treatment probe
Treatment Time	10 minutes
Target Size	Line pattern, manually scanned over area of treatment

DEVICE SPECIFICATIONS

Figure 1 below contains an image of the Erchonia HLS Laser, and a description of the system components follows.

Figure 1: The Erchonia HLS Laser

#1 POWER BUTTON (ON/OFF)

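### As worded, the week 8 endpoint data and the only satisfaction rating may come from completers alone, because no assessment is scheduled for a subject who stops early

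*Combined protocol and SAP*

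**What the plan says.** Three evaluations follow the start of treatment, and each is introduced by an amount of laser use:

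- 2 Week Evaluation: "Following 2 weeks of study procedure administrations with the Erchonia® HLS™, the following will be recorded over videoconference or telemedicine". THI, both NRS scales and adverse events are listed.
- 4 Week Evaluation: "Following 4 weeks of study procedure administrations with the Erchonia® HLS™, the following will be recorded over videoconference or telemedicine". The list is the same.
- 8 Week Evaluation: Study Endpoint: "Following 8 weeks of study procedure administrations with the Erchonia® HLS™, the following will be recorded over videoconference or telemedicine". The list is the same, with the satisfaction rating added.

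The last of these sections makes its own recordings the endpoint: "These recordings will form the study endpoint data set from which change from baseline will be evaluated with respect to assessing study outcome".

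Under Subject Satisfaction with Study Outcome, the subject is asked how "satisfied he or she is with any change in his or her overall tinnitus following completion of the laser administration procedures". The rating appears in neither the week 2 nor the week 4 list.

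The Procedure Administration Protocol has every subject receiving 56 daily home sessions over 8 weeks. The Statistical Analysis section lists baseline and weeks 2, 4 and 8 as time points, plans descriptive and trend presentation with an optional ANCOVA, and sets no success criteria. The protocol has no early-termination visit, no statement on following subjects who stop using the device, no analysis set and no rule for missing data.

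**The concern.** Treatment is open-label, daily, unsupervised and unpaid for eight weeks, so some stopping is foreseeable. Suppose a subject gives up in week 3. Taken at its word, the trigger for the week 4 and week 8 calls is never met for that person. There would be no week 8 THI or NRS value and no satisfaction rating, and nothing in the plan asks for the reason.

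If people stop because the laser does not help or irritates the skin (irritation is among the possible events listed under Adverse Events), the week 8 summaries cover those content enough to finish. Values that were never collected cannot be recovered at analysis. This is most acute for satisfaction, which has no earlier measurement to fall back on.

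The Statistical Analysis section says the results may help in developing a controlled study. Week 8 change, satisfaction and retention are likely to be what that study draws on.

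**Working it through.** The plan states no power, effect size, SD or dropout allowance, so it has no figure on this point to reproduce. Its simple counts agree: 5 + 5 = 10 subjects and 7 x 8 = 56 sessions.

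**Inputs from the protocol.** N = 10, with 5 per group (Sample size).

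**Inputs assumed, because the protocol gives none.** Stopping rate p; number of stoppers k; mean THI change C in completers and S in stoppers (negative is improvement). Reporting by mean change and percentage satisfied is also assumed, since the plan says only that presentation is descriptive.

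**1. Chance of at least one stopper among 10:** 1 - (1 - p)^10

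| p | Chance |
|---|---|
| 5% | 40% |
| 10% | 65% |
| 20% | 89% |
| 30% | 97% |

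**2. Completers' mean against the mean for all enrolled.** The all-enrolled mean is [(10 - k)C + kS]/10, so completers minus all enrolled is k(C - S)/10. With C = -20:

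| Stoppers' change S | k = 1 | k = 2 | k = 3 |
|---|---|---|---|
| +10 (worse) | -3 | -6 | -9 |
| 0 | -2 | -4 | -6 |
| -20 (as completers) | 0 | 0 | 0 |
| -40 (better) | +2 | +4 | +6 |

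A negative entry means that the completers' mean looks too favourable. In the S = 0 row the all-enrolled means are -18, -16 and -14, so -20 overstates the change by 20/18 - 1 = 11%, 20/16 - 1 = 25% and 20/14 - 1 = 43%. Within a group of 5, one stopper with no change gives (4 x -20 + 0)/5 = -16, a gap of 4 points.

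**3. Satisfaction, with 6 satisfied completers:**

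| k | Of completers | Of 10, no stopper satisfied | Of 10, every stopper satisfied |
|---|---|---|---|
| 1 | 6/9 = 67% | 60% | 70% |
| 2 | 6/8 = 75% | 60% | 80% |
| 3 | 6/7 = 86% | 60% | 90% |

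So one or two stoppers can move the summary visibly, and the direction depends on why they stopped. The plan collects nothing that would show which row of the table applies.

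**The case against.** The best defence is that the wording is loose, not restrictive. The Procedure Administration Protocol describes the phase as eight consecutive weeks, and Evaluation Time Points names the visits by week. A site could reasonably read them as calendar visits and call a subject who has stopped. The question actually put to subjects about satisfaction asks about change after the study procedures, which someone who stopped could answer. The Expected Results sentence, "Following completion of the study procedure administration protocol with the Erchonia® HLS™", states what is anticipated and defines no visit or data set. This is also an uncontrolled pilot of 10 subjects with no success criteria, where missing subjects are easy to show.

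Much of this stands, and it rules out three stronger readings that a reader might infer:

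- **That early stoppers are excluded from the results.** No section says so. The analysis covers outcomes at all time points, so the week 3 stopper's week 2 THI and NRS values remain in the trend presentation. Only later values, and above all week 8 change and satisfaction, are at risk.
- **That their safety data are lost.** Under Adverse Events, whatever a subject reports during the trial is recorded and independently reviewed. Only the scheduled prompts may lapse.
- **That week 8 change and satisfaction will look too good.** The direction is plausible but not established. The 11% to 43% range holds only if completers improve and every stopper has zero change.

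The defence does not supply the missing instruction. Even on a calendar reading, no section says that the calls are held with someone who has stopped, or how a missing week 8 value is reported.

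**Conclusion.** The point holds in a limited form. Read literally, the endpoint set and the only satisfaction rating depend on 8 weeks, or completion, of laser use, and nobody who stops early has a scheduled assessment. Week 8 change and satisfaction may therefore describe completers only.

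The size cannot be fixed from the documents. Each stopper is 10% of the sample and 20% of a group. Under the assumed completer change of -20 and no change in stoppers, each stopper shifts the overall mean by 2 points. The shift is nil if stoppers respond like completers, and it reverses if they stopped because they had improved more.

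This is a cheap improvement worth making before enrolment, because the data cannot be collected afterwards. It does not show that the pilot's results will be biased.

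**What to change.** Revise Subject Satisfaction with Study Outcome, the three evaluation sections and Statistical Analysis as follows.

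1. Date the week 2, 4 and 8 evaluations from the first session, and seek them from every enrolled subject whether or not laser use continues.
2. When a subject stops, record the reason and take THI, both NRS scales, satisfaction and adverse events on that call. Still attempt the calendar week 8 call. Its values enter the endpoint set, and the values taken at stopping are shown separately.
3. Report the number assessed out of 10 enrolled and out of 5 in each group. Give satisfaction as counts out of 10, with missing as its own category.
4. Give mean change on the observed week 8 values, with a simple sensitivity summary beside it, for example using the last recorded value or zero change for missing subjects. Dividing observed change by 10 should not be the main result, since it silently gives missing subjects a change of zero.

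The cost is a wording change and a few short remote calls. Visits are already remote and the THI takes 10 minutes. Some subjects who have stopped may decline. Nothing here sets a rule on when treatment should stop.
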